7.8. Treatment after the End of the Study

MP-101 will not be made available to patients after conclusion of the study.

8. Discontinuation Criteria

8.1. Discontinuation from Study Treatment

8.1.1. Permanent Discontinuation from Study Treatment

Discontinuation of dosing for abnormal liver tests should be considered by the investigator when a patient meets 1 of the following conditions, after consultation with the Sponsor designated medical monitor:

- alanine aminotransferase (ALT) or aspartate aminotransferase (AST) >8 × upper limit of normal (ULN)
- alanine aminotransferase or AST >5 × ULN for more than 2 weeks
- alanine aminotransferase or AST >3 \times ULN and total bilirubin level (TBL) >2 \times ULN or prothrombin time >1.5 \times ULN
- alanine aminotransferase or AST >3 × ULN with the appearance of fatigue, nausea, vomiting, right upper-quadrant pain or tenderness, fever, rash, and/or eosinophilia (>5%)
- alkaline phosphatase (ALP) >3 × ULN
- alkaline phosphatase $>2.5 \times ULN$ and TBL $>2 \times ULN$
- alkaline phosphatase >2.5 × ULN with the appearance of fatigue, nausea, vomiting, right-quadrant pain or tenderness, fever, rash, and/or eosinophilia (>5%)

In addition, patients will be discontinued from the investigational product in the following circumstances:

- the occurrence of worsening psychosis and/or agitation or aggression requiring rescue therapy
- the occurrence of an SAE that in the opinion of the investigator would preclude the patient from continuing in the study
- the occurrence of a clinically significant event, which is defined as a moderate (Grade 2) AE, laboratory result, ECG finding, or vital sign change based on the Common Terminology Criteria for Adverse Events v4.03 (CTCAE) or most current version, that in the opinion of the investigator would preclude the patient from continuing in the study. Clinically significant events of special interest include vomiting or "dizziness" associated with balance and gait instability as assessed for ambulatory patients using the TUG test

For patients who discontinue the investigational product early, sites will make every reasonable effort to ensure that patients have procedures performed as shown in the Schedule of Activities (Section 2).

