6.4. Screen Failures

Individuals who do not meet the criteria for participation in this study (screen failure) may be re-screened 1 time with sponsor approval. The time period from screen fail to rescreen will be determined by the investigator. If rescreening is performed, a new informed consent form (ICF) must be signed, and the patient will be assigned a new identification number. Additionally, all screening procedures must be conducted at rescreen to ensure all eligibility criteria are met.

At screening and throughout the study, procedure/lab retests may be conducted at the discretion of the investigator and do not constitute a rescreen.

7. Treatment

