9.4.6. Safety Monitoring

The Mediti Pharma, Inc. CRP or designee, and Chorus will monitor safety data throughout the course of the study. Chorus will oversee the formal and periodic safety reviews conducted during the study.

These safety reviews include the review of SAEs within time frames mandated by company procedures, as well as the review of evolving aggregate safety data within the study by appropriate methods. This review will include the assessment of:

- trends in safety data
- adverse events including monitoring of vomiting or dizziness associated with balance and gait instability as assessed using the TUG test

If a patient experiences elevated ALT $\ge 3 \times \text{ULN}$, ALP $\ge 2 \times \text{ULN}$, or TBL $\ge 2 \times \text{ULN}$, clinical and laboratory monitoring should be initiated by the investigator and continue until resolution with further treatment as clinically indicated. To ensure patient safety and comply with regulatory guidance, the investigator is to consult with the Mediti Pharma, Inc. CRP or designee regarding collection of specific recommended clinical information and follow-up laboratory tests (see Appendix 4).

In the event that safety monitoring uncovers an issue that needs to be addressed by unblinding at the group level, only members of the Assessment Committee (see Section 10.3.7) can conduct additional analyses of the safety data. Furthermore, the entire study may be stopped in the event of safety concerns over drug related adverse events.

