9.5. Pharmacokinetics

9.5.1. Pharmacokinetic Sampling

At the visits and times specified in the Schedule of Activities (Section 2), venous blood samples will be collected from all patients, for a total of 5 scheduled samples per patient, to determine the plasma concentrations of MP-101, and its primary active metabolite LY2812223. The sparse sampling scheme in Table 9.1 will be used.

Table 9.1.	Plasma Pharmacokinetic Sampling Scheme
------------	--

Week	Visit	Sample Collection Time Intervals
2	4	4 to 8 hours postdose
4	5	Predose and 0 to 2 hours postdose
6	6	8 to 12 hours postdose
10	8	2 to 4 hours postdose

The actual sample collection date and time (24-hour clock time) must be recorded, as well as the date and time of the 2 most recent doses. If a patient discontinues early, a sample should be taken at the early termination visit, if possible.

Samples are to be collected at specific time intervals relative to dose administration; therefore, visits that include timed PK testing (Visits 4, 5, 6, and 8 [Weeks 2, 4, 6, and 10, respectively]) must be scheduled relative to the patient's dosing schedule. During Visit 5 (Week 4), the first PK sample will be taken predose; the dose will be administered and another PK sample will be taken up to 2 hours postdose. For all visits that include PK sampling, the approximate start and stop times of food consumption prior to dosing and up to 4 hours postdose will be recorded.

Additional PK samples may be collected at additional time points during the study if warranted and agreed upon between both the investigator and sponsor.

Instructions for the collection and handling of blood samples will be provided by the sponsor.

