Appendix 2. Clinical Laboratory Tests

Laboratory Tests

Clinical Chemistrya,b

Serum Concentrations of:

Sodium

Potassium

Total bilirubin

Direct bilirubin

Alkaline phosphatase

Alanine aminotransferase (ALT)

Aspartate aminotransferase (AST)

Blood urea nitrogen (BUN)

Creatininec

Uric acid

Calcium

Glucose

Albumin

Total Protein

Creatine kinase (CK)

Cystatin-C

Complete Blood Count with differential

Urine dipstickd

Serology a,b

Hepatitis C Antibody

HIV

Hepatitis B Surface Antigen

Other Tests^a

FSHe

Pharmacokinetica

MP-101 and LY2812223 plasma concentrations

Abbreviations: CKD-EPI= Chronic Kidney Disease Epidemiology Collaboration; FSH = follicle stimulating hormone; HIV = human immunodeficiency virus.

- a Assayed by sponsor-designated laboratory
- b Unscheduled or repeat blood chemistry, hematology, and urinalysis panels may be performed at the discretion of the investigator, as needed.
- c Estimated glomerular filtration rate will be calculated using serum creatinine values and the CKD-EPI Cystatin C Equation (Grubb et al. 2010; Peralta et al. 2011; Inker et al. 2012).
- d Microscopic examination of sediment performed only if abnormalities are noted on the routine urinalysis.
- e To confirm postmenopausal status for women ≥50 and <60 years of age who have had a cessation of menses, an FSH test will be performed. Non-childbearing potential is defined as an FSH ≥40 mIU/mL and a cessation of menses for at least 12 months.

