Appendix 4. Hepatic Monitoring Tests for Treatment-Emergent Abnormality

Selected tests may be obtained in the event of a treatment-emergent hepatic abnormality and may be required in follow-up with patients in consultation with Mediti Pharma, Inc. or its designee clinical research physician.

Henatic	Mon	itoring	Tests
HUDAUC	TATOR	Ituline	1 (313

Hepatic Hematology ^a	Haptoglobin ^a	
Hemoglobin		
Hematocrit	Hepatic Coagulation ^a	
RBC	Prothrombin Time	
WBC	Prothrombin Time, INR	
Neutrophils, segmented		
Lymphocytes	Hepatic Serologies ^{a,b}	
Monocytes	Hepatitis A antibody, total	
Eosinophils	Hepatitis A antibody, IgM	
Basophils	Hepatitis B surface antigen	
Platelets	Hepatitis B surface antibody	
	Hepatitis B Core antibody	
Hepatic Chemistry ^a	Hepatitis C antibody	
Total bilirubin	Hepatitis E antibody, IgG	
Conjugated bilirubin	Hepatitis E antibody, IgM	
Alkaline phosphatase		
ALT	Anti-nuclear antibody ^a	
AST		
GGT	Anti-smooth muscle antibody (or anti-actin	
CPK	antibody) ^a	

Abbreviations: ALT = alanine aminotransferase; AST = aspartate aminotransferase; CPK = creatinine phosphokinase; GGT = gamma-glutamyl transferase; Ig = immunoglobulin; INR = international normalized ratio; RBC = red blood cells; WBC = white blood cells.

- ^a Assayed by Mediti Pharma, Inc.-designated or local laboratory.
- b Reflex/confirmation dependent on regulatory requirements and/or testing availability

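### The liver-monitoring trigger in Section 9.4.6 omits AST, which every transaminase criterion in Section 8.1.1 includes; separately, no retest interval backs the 2-week persistence criterion for either enzyme

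*Protocol*

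**What the plan says.** Protocol Section 8.1.1 opens its liver rules with "Discontinuation of dosing for abnormal liver tests should be considered by the investigator when a patient meets 1 of the following conditions"; the medical monitor is to be consulted first. Four of the conditions concern transaminases, and all four name both enzymes:

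- ALT or AST >8 × ULN;
- "alanine aminotransferase or AST >5 × ULN for more than 2 weeks";
- ALT or AST >3 × ULN with total bilirubin >2 × ULN or prothrombin time >1.5 × ULN;
- ALT or AST >3 × ULN with listed symptoms or eosinophilia.

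Section 9.4.6 sets the monitoring trigger. It begins "If a patient experiences elevated ALT", gives a limit of ≥3 × ULN, and adds ALP ≥2 × ULN and total bilirubin ≥2 × ULN. AST does not appear. Once triggered, "clinical and laboratory monitoring should be initiated by the investigator and continue until resolution", and the investigator consults the sponsor's physician about the follow-up tests in Appendix 4. No retest interval is given.

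Three other places allow repeats:

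- Section 6.4, which covers both screening and treatment: "procedure/lab retests may be conducted at the discretion of the investigator and do not constitute a rescreen".
- Appendix 2: "Unscheduled or repeat blood chemistry, hematology, and urinalysis panels may be performed at the discretion of the investigator".
- Appendix 4: "Selected tests may be obtained in the event of a treatment-emergent hepatic abnormality and may be required in follow-up with patients". The sponsor's or designee's physician is consulted on this.

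The Schedule of Activities places on-treatment chemistry at Visits 4, 6 and 8 (Weeks 2, 6 and 10), plus early termination.

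**The concern.** AST is measured at every scheduled chemistry and can justify considering discontinuation, yet on its own it never starts the monitoring that would show whether such a condition is met. The same rise in ALT would start monitoring and bring in the sponsor's physician. The protocol gives no reason for the difference.

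Two 8.1.1 conditions need information beyond a single chemistry result. The persistence condition needs a later value. The prothrombin-time limb needs a test that is in Appendix 4 but not in the scheduled panel of Appendix 2. For an isolated AST rise, nothing requires either before the next scheduled draw.

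At stake is the safety of a few patients. Someone with a persistent rise could stay on drug past the point at which the protocol itself asks whether dosing should go on. No endpoint, power or type I error is affected.

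**Working it through.** The plan states no figure on this point, so there is none to reproduce. The check compares the two rules and then measures the schedule against the 2-week criterion.

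**Step 1. Analytes in each rule.**

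| Analyte | Condition in 8.1.1 | Trigger in 9.4.6 |
|---|---|---|
| ALT | all four transaminase conditions | ≥3 × ULN |
| AST | all four transaminase conditions | none |
| ALP | three conditions | ≥2 × ULN |
| Total bilirubin | with transaminases or ALP | ≥2 × ULN |
| Prothrombin time | with ALT or AST >3 × ULN | none; listed in Appendix 4 only |

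The AST gap is confined to patients with raised AST, no listed symptom or eosinophilia, and ALT <3, ALP <2 and bilirubin <2 × ULN. Any other pattern triggers 9.4.6 or meets an 8.1.1 condition directly.

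**Step 2. Interval between scheduled chemistry draws.** Target days are 14, 42 and 70, each with a window of ±2 days.

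- Week 2 to Week 6: 42 − 14 = 28 days.
- Week 6 to Week 10: 70 − 42 = 28 days.
- With both windows: 28 − 4 = 24 to 28 + 4 = 32 days.

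**Step 3. Time past the 2-week limit**, counting from the first raised value.

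- At target: 28 − 14 = 14 days.
- Range: 24 − 14 = 10 to 32 − 14 = 18 days.
- Share of the 70-day treatment period: 14/70 = 20% (10/70 = 14% to 18/70 = 26%).

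A rise first seen at Week 6 is next checked by schedule at Week 10, when treatment ends.

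**Step 4. What causes the delay.** Steps 2 and 3 do not depend on the enzyme. With ALT, 9.4.6 at least tells the investigator to monitor, which makes an earlier repeat likely but fixes no date. Adding AST to the trigger would give AST that same prompt and no more.

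**Step 5. Would a repeat at Visit 5 be enough?** Visit 5 is a site visit with blood sampling ("During Visit 5 (Week 4), the first PK sample will be taken predose") but no chemistry panel. It falls 28 − 14 = 14 days after Week 2 at target, range 14 − 4 = 10 to 14 + 4 = 18. The criterion asks for more than 2 weeks, so a repeat at target just misses it. If the five integer days in each window are taken as equally likely (an assumption), the interval exceeds 14 days only when Visit 5 falls later in its window than Visit 4 did in its own: 10 of 25 combinations, or 40%. The last permitted day for Visit 5 is 28 + 2 = Day 30. After a Week 2 draw on Day 15 or earlier, Visit 5 can be placed at least 30 − 15 = 15 days later. After a draw on Day 16 it cannot, since 30 − 16 = 14.

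**The case against.** The strongest reply is that other provisions already cover this patient and that the 14-day figure is charged to the wrong cause.

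- **Other provisions.** Section 8.1.1 also discontinues patients for a Grade 2 laboratory result that the investigator judges incompatible with continuing, with no 2-week wait. Section 9 requires timely, documented review of laboratory reports. Section 9.2 requires follow-up of AEs that are serious, medically important or considered related. Retests are allowed at any time. All of this stands as mitigation, but none of it requires a repeat by a given date: the Grade 2 clause rests on opinion, and Section 9.2 leaves the frequency of follow-up to the investigator.
- **Symptoms.** Visit 5 and the Week 8 call both include AE assessment. Nausea, vomiting or fatigue found there with AST >3 × ULN would meet the fourth condition. Section 3 lists nausea, vomiting and tiredness among the most common AEs. This stands and narrows the case to patients without symptoms.
- **Prior experience.** Section 3 reports no significant safety-laboratory changes in earlier studies. The predicted peak concentration at 60 mg with eGFR 45 is about a third of that observed at 400 mg (3600/10900 = 0.33). This supports a low expected risk, but those data come from healthy men dosed for up to 14 days, not patients aged 50 or older dosed for 10 weeks.
- **Choice of ALT.** AST can rise for reasons outside the liver, so an ALT trigger is defensible in itself. It sits badly, however, with stopping conditions that treat the two enzymes alike.
- **Cause of the delay.** A reader might infer that leaving AST out delays confirmation by 14 days. The documents do not support that: the delay comes from the chemistry schedule and the missing retest interval, which apply to ALT as well.

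**Conclusion.** There are two minor gaps, and they should be kept apart.

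1. Section 9.4.6 omits AST. An isolated, asymptomatic AST rise therefore starts no required monitoring or sponsor consultation, and nothing requires the prothrombin time that one 8.1.1 condition uses.
2. For ALT and AST alike, no retest interval supports the 2-week persistence condition. Confirmation may come about 14 days (10–18) late.

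The second figure assumes that the 2 weeks run from the first raised value, that visits fall within their windows, and that nobody retests before the next scheduled draw. The delay is therefore possible, not certain. A reader might also infer that a mandatory stop is postponed. It is not, because the liver conditions call only for discontinuation to be considered. AST >8 × ULN, or >3 × ULN with listed symptoms, can be acted on at the first draw.

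The omission and the schedule gaps can be read directly from the text. How often such a patient would arise is unknown.

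**What to change.** In Section 9.4.6:

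- Change the trigger to ALT or AST ≥3 × ULN, with the limit confirmed by the sponsor's medical monitor. Consultation on the Appendix 4 tests, which include prothrombin time, then follows for either enzyme.
- State that any ALT or AST >5 × ULN is repeated promptly and, if still raised, again just after 14 days from the first value, for example 15 to 17 days after it. Use Visit 5 for this only if it falls more than 14 days after the first draw; otherwise arrange an unscheduled draw. For a rise first seen at Week 6, the later repeat needs an unscheduled visit, because Week 8 is a telephone contact.

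The first change without the second would not secure the 2-week check. The cost is one or two sentences and an occasional extra blood draw or visit, including for AST rises that do not come from the liver. Creatine kinase, already in the panel, helps to identify those.

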8.1.2. Discontinuation of Inadvertently Enrolled Patients

If the sponsor or investigator identifies a patient who did not meet enrollment criteria and was inadvertently enrolled, a discussion must occur between the Mediti Pharma, Inc. CRP or designee and the investigator to determine if the patient may continue in the study. If both agree it is medically appropriate to continue, the investigator must obtain documented approval from the Mediti Pharma, Inc. CRP or designee to allow the inadvertently enrolled patient to continue in the study with or without treatment with investigational product.

8.2. Discontinuation from the Study

Patients may be discontinued in the following circumstances:

- enrollment in any other clinical trial involving an investigational product or enrollment in any other type of medical research judged not to be scientifically or medically compatible with this study
- participation in the study needs to be stopped for medical, safety, regulatory, or other reasons consistent with applicable laws, regulations, and good clinical practice (GCP)
- investigator decision
 - o the investigator decides that the patient should be discontinued from the study
 - o if the patient, for any reason, requires treatment with another therapeutic agent that is intended for the treatment of psychosis, discontinuation from the study occurs prior to introduction of the new agent
- patient decision
 - o the patient and/or caretaker requests patient withdrawal
- sponsor decision

If a patient discontinues the study early, the site will make every reasonable effort to have the patient return for an early termination visit to have end-of-study procedures performed as shown in the Schedule of Activities (Section 2). If the patient does not return, this will not be considered a protocol deviation.

8.3. Patients Lost to Follow-up

A patient will be considered lost to follow-up if he or she repeatedly fails to return for scheduled visits and is unable to be contacted by the study site. Site personnel are expected to make diligent attempts to contact patients who fail to return for scheduled visits or were otherwise unable to be followed up by the site.

9. Study Assessments and Procedures

Section 2 lists the Schedule of Activities, detailing the study procedures and their timing.

Appendix 2 lists the laboratory tests that will be performed for this study.

Unless otherwise stated in subsections below, all samples collected for specified laboratory tests will be destroyed within 60 days of receipt of confirmed test results. Certain samples may be retained for a longer period, if necessary, to comply with applicable laws, regulations, or laboratory certification standards.

Investigators must document their timely review of each laboratory safety report.

9.1. Efficacy Assessments

9.1.1. Primary Efficacy Assessment

The primary endpoint is the response on the NPI-Psychosis subscale items of delusions and hallucinations and/or the agitation/aggression domain.

Neuropsychiatric Inventory (NPI; Cummings et al. 1994).

The NPI is a tool for assessing psychopathology in patients with brain disorders (i.e., AD and other dementias). Information is obtained from an informed caregiver who is familiar with the patient's behavior. Ten behavioral and 2 neurovegetative areas are included in the NPI: delusions, hallucinations, agitation/aggression, depression/dysphoria, anxiety, elation/euphoria, apathy/indifference, disinhibition, irritability/lability, aberrant motor behavior, sleep and nighttime behavior disorders and appetite and eating disorders. An initial question assesses the 10 items and 2 neurovegetative evaluations of the scale. If the answer to the initial question is 'no', no further questions are pursued. If the answer is 'yes', sub questions are asked; ratings of the frequency and severity of the behavior(s) are determined by the caregiver according to the criteria provided with each behavior. Distress induced in the caregiver by each behavior is also rated. Therefore, a total of 4 scores are computed for each behavior type: frequency, severity, total (frequency × severity), and caregiver distress (Cummings 2009).

9.1.2. Secondary Efficacy Assessments

The secondary endpoints are listed below.

Clinical Global Impression of Improvement (CGI-I; Guy et al. 1976)

The CGI-I is a 7-point scale that requires the clinician to assess how much the patient's illness has improved or worsened relative to baseline (Visit 2). The scale ranges from 1 (very much improved) to 7 (very much worse).

Neuropsychiatric Inventory (NPI; Cummings et al. 1994)

Neuropsychiatric disturbances, caregiver distress, and other key parameters of patient behavior in this study will be measured using the NPI total score, the NPI Domains of anxiety, sleep and

nighttime behavior disorders, and the NPI Caregiver Distress (NPI-D) score. A detailed description of NPI scoring can be found in Section 9.1.1.

Mini-Mental State Examination (MMSE; Folstein et al. 1975)

The MMSE is a brief assessment used to assess cognitive function. The assessment is a simple, 30-question, pen-and-paper test that evaluates attention, orientation, memory, registration, recall, calculation, language, and the ability to draw a complex polygon (Arevalo-Rodriguez et al. 2015). The range for the total MMSE score is 0 to 30, with lower scores indicating greater impairment.

Unified Parkinson's disease Rating Scale Part III (UPDRS; Fahn, 1987)

Part III of the UPDRS is an investigator-scored scale used to assess the motor symptoms of patients with Parkinson's disease. The investigator indicates if the patient is receiving medication for treating Parkinson's disease symptoms (specifically levodopa, and the time since the last dose) and the patient's clinical response to the medication. The investigator rates the patient on 14 items based on observation or the performance of a task the patient performs (even in the context of any comorbidities) on a 5-point scale. The scores range from 0 to 4, with higher scores indicate greater impairment.

